12.6 Safety Analyses

All safety analyses will be summarized by dose level, regardless of phase and all doses combined, by phase, in the Safety population.

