5.2 Endpoints

5.2.1 Primary Endpoints

- Incidence of dose limiting toxicities (DLTs) occurring during the first 28-day cycle of combination treatment.
- Objective response rate (ORR) defined by RECIST 1.1.

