Note that the DLT evaluation period does not include the 7 day run in of mocetinostat.

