7.4 Safety Population

The safety population is defined as all patients who received at least 1 dose of either mocetinostat or durvalumab. The safety population will be used for all safety analyses.

Sponsor: Mirati Therapeutics, Inc.

Protocol no: 0103-020

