7.5 DLT Evaluatable Population

For a patient to be considered evaluable for dose-escalation decisions, or “DLT-evaluable,” the patient must have either been on study for 1 full cycle and have received treatment with durvalumab and at least 9 of 12 scheduled mocetinostat doses (75%) in Cycle 1 or have experienced a DLT in Cycle 1.

Note that the DLT evaluation period does not include the 7 day run in of mocetinostat.

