12.0 Statistical Methods

All data collected during this study will be displayed in data listings, unless otherwise specified. Data listings will be sorted by dose level and patient identifier (regardless of phase) for safety listings and by

Sponsor: Mirati Therapeutics, Inc.

Protocol no: 0103-020

phase, dose level/cohort, and patient identifier for efficacy. Screen failures will be excluded from all tables and listings. In addition, listings will include all relevant derived variables.

Descriptive statistics (mean, median, standard deviations [STD], minimum and maximum values) for continuous variables will be presented. Mean and median will be presented to 1 decimal more than original data. STD will be presented to 2 decimals more than original data. Minimum and maximum will match the decimal points in the original data. For categorical variables, summary measures will include the frequency and percentage (with 1 decimal place) of patients in each category.

The summary tables will be presented by dose level (both phases combined) for safety and by phase and dose level/cohort for efficacy.

Unless otherwise noted, missing data will not be imputed or carried forward.

All data summaries and tabulations will be prepared with SAS® Version 9.4 or higher.

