12.1 Patient Disposition

The number and percentage of patients enrolled and treated in the study will be presented, together with the number and percentage of patients who withdrew from the study prematurely and a breakdown of the corresponding reasons for withdrawal and the number and percentage of patients who discontinued mocetinostat and durvalumab with the corresponding reasons. will be reported by category for each phase and dose level/cohort, as well as overall within each phase. Additionally the number of patients in the mITT, Clinical activity evaluable, Safety, and DLT Evaluable populations will be presented.

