12.6.1 Adverse Events

A summary of TEAEs, including the number and percentage of DLTs, number and percentage of patients reporting at least one TEAE, the number and percentage of patients reporting at least one CTCAE Grade 3 or greater TEAE, the number and percentage of patients discontinuing due to a TEAE, the number and percentage of patients with at least one serious adverse event (SAE), number and percentage of patients with at least one SAE by CTCAE grade, number and percentage of patients with at least 1 moccetinostat related TEAE, number and percentage of patients with at least 1 durvalumab related TEAE, number and percentage of patients with at least 1 TEAE related to both durvalumab and moccetinostat, number and percentage of patients with at least 1 moccetinostat related SAE, number and percentage of patients with at least 1 durvalumab related SAE, number and percentage of patients with at least 1 SAE related to both durvalumab and moccetinostat, number and percentage of patients discontinuing moccetinostat due to a TEAE, number and percentage of patients discontinuing durvalumab due to a TEAE, number and percentage of patients discontinuing moccetinostat due to a TEAE related to moccetinostat, number and percentage of patients discontinuing durvalumab due to a TEAE related to durvalumab, and the number and percentage of deaths will be presented. TEAEs are those that first occur or increase in severity or relationship to study treatment after the first dose of study treatment and not more than 30 days after the last dose of study treatment. In reality, all adverse events that change in severity or relationship to study treatment are assigned a new start date and captured as a new record. All AEs will be coded according to the MedDRA Version 19.0 dictionary by SOC, PT, and severity grade using NCI CTCAE Version 4.03.

A breakdown of the number and percentage of patients reporting each adverse event categorized by SOC and PT will be presented. Note that counting will be by patient not event and patients are only counted once within each SOC or PT. Similar summaries for CTCAE Grade ≥ 3 TEAEs, moccetinostat-related TEAEs, durvalumab-related TEAEs, CTCAE Grade ≥ 3 moccetinostat-related TEAEs, and CTCAE Grade ≥ 3 durvalumab-related TEAEs will be presented.

Sponsor: Mirati Therapeutics, Inc.

Protocol no: 0103-020

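### The only planned summary of the primary DLT endpoint uses the Safety population with both phases pooled by dose level, so its percentage need not equal the Phase 1 rate in DLT-evaluable patients

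*SAP*

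**What the plan says.** SAP 5.2.1 lists as one of two primary endpoints: "Incidence of dose limiting toxicities (DLTs) occurring during the first 28-day cycle of combination treatment". In Section 12 the only summary of it is in 12.6.1, which opens: "A summary of TEAEs, including the number and percentage of DLTs".

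Three statements fix the denominator and layout of that item:

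- SAP 7.4: "The safety population will be used for all safety analyses". This population takes in anyone given at least one dose of either drug.
- SAP 12.0: "The summary tables will be presented by dose level (both phases combined) for safety".
- SAP 12.6: "All safety analyses will be summarized by dose level, regardless of phase and all doses combined, by phase, in the Safety population".

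SAP 7.5 defines a DLT-evaluable population for dose-escalation decisions. There are two ways to qualify: "have received treatment with durvalumab and at least 9 of 12 scheduled mocetinostat doses (75%) in Cycle 1 or have experienced a DLT". The first way also requires completing the cycle, and for the second the event must fall within Cycle 1. SAP 6.1.1 adds: "Note that the DLT evaluation period does not include the 7 day run in of mocetinostat". Section 12 uses this population once, in 12.1: "Additionally the number of patients in the mITT, Clinical activity evaluable, Safety, and DLT Evaluable populations will be presented".

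Elsewhere the SAP names an evaluable population where it wants one: the clinical activity evaluable population for the primary ORR analysis (12.5.1) and the ADA-evaluable population for ADA (12.5.3). The protocol does not fill the gap. Sections 9.3.3 and 9.3.4 repeat the Safety rule and the DLT-evaluable definition, and 9.5.1 specifies no DLT table.

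**The concern.** The denominator of a DLT rate should hold the patients who could have been counted as having a DLT. Here the general safety rule supplies the denominator by default, and it admits patients whom SAP 7.5 deliberately leaves out.

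The column layout adds to the problem. By-dose columns merge the phases and the by-phase column merges the doses, so no planned column shows Phase 1 DLT incidence at a given dose. What is at stake is the reported value of a primary endpoint: a reader of the study report could take a diluted percentage for the toxicity rate at a dose level.

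**Working it through.** The plan states no figure for this endpoint, so there is none to reproduce. The check is a reading of the rules followed by simple proportions. All DLT counts and non-evaluable counts below are assumptions.

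**Inputs from the documents**
- Six patients is the minimum experience for declaring the MTD (SAP 6.1.3).
- With six patients, the mTPI grid gives the stay decision for 1 or 2 DLTs (Protocol Appendix 2).
- Phase 2 Stage 1 targets are 9 evaluable patients in each of Cohorts 1, 3 and 4, and about 17 in Cohort 2 (SAP 6.2). In total 9 + 9 + 9 + 17 = 44.

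**Step 1: who can be in the numerator.** Under SAP 7.5 a Cycle 1 DLT makes a patient evaluable automatically. A non-evaluable Phase 1 patient therefore has no Cycle 1 DLT. A patient who received only the lead-in never entered the DLT window. Both kinds belong to the Safety population.

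**Step 2: Phase 1 patients alone.** Let d be the patients with a DLT, n the DLT-evaluable patients and m the other treated Phase 1 patients at that dose. The DLT-evaluable rate is d/n; the Safety-population rate is d/(n + m). With n = 6:

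| d | d/6 | m = 1 | m = 2 | m = 3 |
|---|---|---|---|---|
| 0 | 0% | 0% | 0% | 0% |
| 1 | 16.7% | 1/7 = 14.3% | 1/8 = 12.5% | 1/9 = 11.1% |
| 2 | 33.3% | 2/7 = 28.6% | 2/8 = 25.0% | 2/9 = 22.2% |

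If d = 0 or m = 0 there is no effect.

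**Step 3: the recommended Phase 2 dose.** Phase 2 uses this dose (SAP 6.0), so its patients fall in the same column. Take n = 6 and m = 2.

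- *DLTs classified only in Phase 1.* With 9 Phase 2 patients (one cohort at its Stage 1 minimum) the denominator is 6 + 2 + 9 = 17, giving 2/17 = 11.8%. With 44 it is 6 + 2 + 44 = 52, giving 2/52 = 3.8%; one DLT gives 1/52 = 1.9%.
- *DLTs also classified in Phase 2.* The column shows (Phase 1 DLTs + Phase 2 DLTs)/52. It could lie either side of the Phase 1 rate and does not estimate Phase 1 alone.

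The 9 and 44 are activity-evaluable targets. The Safety count should be at least similar, because patients who stop before the first disease assessment for an adverse event or withdrawn consent are left out of those targets (SAP 7.3) but stay in the Safety population.

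**Step 4: which case applies.** The DLT definition sits under the Phase 1 portion (SAP 6.1.1) and SAP 6.2 does not mention DLTs, which points to the first case. The endpoint wording in 5.2.1 and the definition in 7.5 carry no phase restriction, so the second case is not excluded.

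**The case against.** The strongest reply is that nothing depends on this percentage. Escalation and the MTD use DLT-evaluable patients and the mTPI grid, and no test or go/no-go rule reads the tabulated rate. That stands. A reader might infer that dose decisions are compromised; the documents do not support this.

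A second reply is that the Phase 1 figures can be recovered. SAP 12.6 also plans an all-doses column by phase. If dose level means assigned dose, every column other than the recommended Phase 2 dose is Phase 1 only, and subtracting those from the Phase 1 total gives the remaining DLT count. SAP 12.1 tabulates the DLT-evaluable head count, and 12.0 and 12.6.1 plan listings. This largely stands, although 12.6.1 does not say whether its DLT item counts events or patients, and a primary endpoint should not need rebuilding.

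Third, a reader might infer that the rate at the recommended Phase 2 dose must collapse to a few percent. That needs DLTs to be unclassified in Phase 2, which the SAP does not settle, so the claim is conditional.

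Fourth, the item in 12.6.1 is not labelled as the primary analysis, and SAP Appendix 2 places the table shells in a separate document that was not available and may contain a DLT-evaluable table. This lowers confidence. It does not remove the point: no sentence in the SAP exempts DLT incidence from the rule for all safety analyses, and shells that differ would conflict with the text.

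**Conclusion.** The point holds on the SAP text, with moderate confidence. The one specified summary of the primary DLT endpoint has a denominator that does not match its numerator.

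- **Within Phase 1** the direction is certain once there is at least one DLT and at least one treated patient who is not DLT-evaluable: the percentage falls. In the assumed cases the fall is from 2.4 points (16.7% to 14.3%) to 11.1 points (33.3% to 22.2%).
- **At the recommended Phase 2 dose** the fall is much larger if DLTs are classified only in Phase 1. If they are classified in both phases, the figure is a mixture with no fixed direction of error.

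This is a defect in reporting a primary endpoint, not in the dose-finding rule, and it should be corrected before database lock.

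**What to change.** Add to SAP 12.6 that the primary DLT endpoint will be reported for Phase 1 patients in the DLT-evaluable population, by mocetinostat dose level, as the number and percentage of patients with at least one Cycle 1 DLT (n/N, %). Then:

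- exempt this analysis from the Safety-population and pooled-phase rules in 7.4, 12.0 and 12.6;
- state whether DLTs are classified in Phase 2 and, if they are, report them separately;
- label the DLT item in the 12.6.1 overview as supportive;
- align the table shells.

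The cost is a few sentences and one table from data already collected. The final SAP version that SAP 4.0 plans before database lock can carry the change. No DLT criterion, dose or clinical rule is touched.

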12.6.1 Adverse Events

A summary of TEAEs, including the number and percentage of DLTs, number and percentage of patients reporting at least one TEAE, the number and percentage of patients reporting at least one CTCAE Grade 3 or greater TEAE, the number and percentage of patients discontinuing due to a TEAE, the number and percentage of patients with at least one serious adverse event (SAE), number and percentage of patients with at least one SAE by CTCAE grade, number and percentage of patients with at least 1 moccetinostat related TEAE, number and percentage of patients with at least 1 durvalumab related TEAE, number and percentage of patients with at least 1 TEAE related to both durvalumab and moccetinostat, number and percentage of patients with at least 1 moccetinostat related SAE, number and percentage of patients with at least 1 durvalumab related SAE, number and percentage of patients with at least 1 SAE related to both durvalumab and moccetinostat, number and percentage of patients discontinuing moccetinostat due to a TEAE, number and percentage of patients discontinuing durvalumab due to a TEAE, number and percentage of patients discontinuing moccetinostat due to a TEAE related to moccetinostat, number and percentage of patients discontinuing durvalumab due to a TEAE related to durvalumab, and the number and percentage of deaths will be presented. TEAEs are those that first occur or increase in severity or relationship to study treatment after the first dose of study treatment and not more than 30 days after the last dose of study treatment. In reality, all adverse events that change in severity or relationship to study treatment are assigned a new start date and captured as a new record. All AEs will be coded according to the MedDRA Version 19.0 dictionary by SOC, PT, and severity grade using NCI CTCAE Version 4.03.

A breakdown of the number and percentage of patients reporting each adverse event categorized by SOC and PT will be presented. Note that counting will be by patient not event and patients are only counted once within each SOC or PT. Similar summaries for CTCAE Grade ≥ 3 TEAEs, moccetinostat-related TEAEs, durvalumab-related TEAEs, CTCAE Grade ≥ 3 moccetinostat-related TEAEs, and CTCAE Grade ≥ 3 durvalumab-related TEAEs will be presented.

Sponsor: Mirati Therapeutics, Inc.

Protocol no: 0103-020

A further summary of the number and percentage of patients reporting each adverse event in at least 10% of patients will be categorized by PT in descending order of frequency.

A summary of events reported categorized by maximum CTCAE grade will also be provided. Patients with multiple events within a particular SOC or PT will be counted under the category of their most severe event within that SOC or PT. Similar summaries for mocetinostat-related TEAEs and durvalumab-related TEAEs will be presented.

Separate summaries of adverse events leading to mocetinostat and durvalumab discontinuation will be provided, grouped by SOC and PT. Separate listings of patients who discontinue mocetinostat and durvalumab due to a TEAE will be presented. Further summaries of mocetinostat-related TEAEs leading to mocetinostat discontinuation and durvalumab-related TEAEs leading to durvalumab discontinuation will be provided.

Pericardial adverse events will be categorized by PT in descending order of frequency. Patients with pericardial events will be listed.

All AEs (including non-treatment-emergent events) recorded on the CRF will be listed.

12.6.2 Deaths and Serious Adverse Events

TEAEs that lead to death will be summarized by SOC and PT. A listing of patients who die will be presented. SAEs will be summarized by SOC and PT. A listing of patients who experience a SAE will also be presented.

Separate summaries for SAEs related to mocetinostat and related to durvalumab grouped by SOC and PT will be presented.

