- 14 Adverse Events: SAEs will be reported from the time of informed consent until 90 days after the last administration of mocetinostat or durvalumab. Adverse events will be reported from the first day of study treatment until at least 28 days after last dose of study drug, and until resolution or stabilization of acute AEs and/or ongoing SAEs. After the 90-day SAE observation period, post-treatment follow-up may be performed by remote contact (e.g., telephone call).
- 15 End of Treatment: Assessments that have been completed in the previous 4 weeks do not need to be repeated (8 or 12 weeks for tumor assessments in accordance with schedule).
- 16 Long Term Follow-up: Blood samples for MEDI4736 PK and ADA will be collected approximately 90 days after the last infusion of durvalumab. Survival status and subsequent therapies will be collected during long term follow-up every 2 months ( $\pm 14$  days) from the date the subject was discontinued from study treatment until death or lost to follow-up. Follow-up beyond 90 days after last treatment may be performed by telephone contact.

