## **8.4 Reporting of SAEs and AEs**

### **8.4.1 Reporting Period**

The active reporting period for SAEs begins from the time that the patient provides informed consent (i.e., prior to undergoing any study-specific procedure or assessment) and continues until 90 days post last administration of either therapy. All SAEs will be followed until the event has resolved or stabilized to a chronic condition, whichever is later. Death must be reported if it occurs during the active reporting period for SAEs regardless of whether a subsequent anticancer therapy is administered. Serious adverse events occurring to a patient after the active reporting period has ended should be reported to the Sponsor if the investigator becomes aware of them and if the investigator assesses at least a reasonable possibility of being related to study drug.

The reporting period for non-serious AEs begins from the day of first dose of study treatment and continues until at least 28 days after last administration of study treatment and/or until recovery from all acute toxicities associated with the drug administration to a chronic condition, whichever is later. If a patient begins a subsequent anticancer therapy, the AE reporting period ends at the time the new treatment is started.

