### **9.5 Safety Data Presentations and Summaries**

#### **9.5.1 Adverse Events**

Adverse events will be classified using the medical dictionary for regulatory activities (MedDRA) classification system. Listings will include the verbatim term, preferred term, and system organ class (SOC). The number of patients with treatment emergent AEs and the incidence of TEAEs by SOC and preferred term will be summarized. TEAEs will be summarized by maximum intensity and relationship to study therapy. Separate summaries will be provided for TEAEs, TESAEs, treatment-related AEs, treatment-related SAEs, and other significant AEs (e.g., AEs leading to study discontinuation).

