8.3.1 Adverse Events

AEs will be coded using Medical Dictionary for Regulatory Activities (MedDRA, Version 15.1 or higher).

Baseline Signs and Symptoms

- Signs and symptoms of the patient's cancer diagnosis and/or comorbidities present on Day 1 of study drug dosing are recorded in the CRF as non-treatment emergent AEs, with actual start date, which will most often predate first dose. Baseline signs and symptoms will be reported separately from TEAEs.

Treatment-Emergent AEs (TEAEs)

- TEAEs are AEs that begin on Day 1 of study treatment or later during the on-study period. Baseline signs and symptoms that change attribution or severity during the on-study period are TEAEs. Any ongoing TEAEs that changes in attribution or severity is captured as a new AE.

Adverse Events of Special Interest (AESI)

AEs of special interest (AESI) for durvalumab based on observed safety event during durvalumab monotherapy and/or class effects for inhibitors of PD-L1 or PD-1 include:

- Colitis
- Pneumonitis
- Alanine aminotransferase (ALT)/aspartate aminotransferase (AST) increases / hepatitis / hepatotoxicity
- Neuropathy / neuromuscular toxicity (i.e., events of encephalitis, peripheral motor and sensory neuropathies, Guillain-Barré, and myasthenia gravis)
- Endocrinopathy (i.e., events of hypophysitis, adrenal insufficiency, and hyper- and hypothyroidism)
- Dermatitis
- Nephritis
- Pancreatitis (or labs suggestive of pancreatitis – increased serum lipase, increased serum amylase).

Immune-related Adverse Event (irAE)

An irAE is defined as an AE that is associated with drug exposure and is consistent with an immune-mediated mechanism of action and where there is no clear alternate aetiology.

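### SAP 12.6.2 tabulates SAEs with no onset limit, so a screening SAE in a patient later dosed enters the all-cause SAE table, where the protocol specifies treatment-emergent SAEs

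*SAP*

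**What the plan says.** Protocol 9.5.1 lists the adverse event tables: "Separate summaries will be provided for TEAEs, TESAEs, treatment-related AEs, treatment-related SAEs, and other significant AEs". The serious-event summary it names is therefore the treatment-emergent one.

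SAP 12.6.2 opens with deaths, limited to treatment-emergent events: "TEAEs that lead to death will be summarized by SOC and PT". The serious-event sentence in the same section carries no such limit: "SAEs will be summarized by SOC and PT. A listing of patients who experience a SAE will also be presented". The SAP specifies no table of treatment-emergent SAEs by SOC and PT.

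SAE collection starts before treatment. Protocol 8.4.1 states: "The active reporting period for SAEs begins from the time that the patient provides informed consent". Footnote 14 of Table 1, the same in both documents, gives both ends: "SAEs will be reported from the time of informed consent until 90 days after the last administration of mocetinostat or durvalumab". Footnote 1 of that table lets consent precede the 28-day screening window.

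The SAP describes treatment emergence twice. Section 8.3.1 says "TEAEs are AEs that begin on Day 1 of study treatment or later during the on-study period" and gives no number of days for the end. Section 12.6.1 ends the window 30 days after the last dose. The overview in 12.6.1 is introduced as a summary of TEAEs, but its SAE rows are not themselves described as treatment-emergent.

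**The concern.** SAEs from the screening period are in the database by design. If the table has no onset rule, a patient hospitalised between consent and the first dose, and then treated, counts as a patient with an SAE in a table headed by dose level.

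Safety and tolerability is a secondary objective, and the trial has no control arm, so the all-cause SAE percentage will be read on its own. A pre-dose event can only move that percentage upward, and the chance of one grows with the time between consent and dosing, which has nothing to do with the drugs.

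There is also a consistency problem. If the overview in 12.6.1 is programmed as treatment-emergent and 12.6.2 is programmed as written, two tables in the same report can give different numbers of patients with an SAE, with nothing in the SAP to explain the gap.

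**Working it through.** The plan states no figure to reproduce. The check is whether any rule removes a pre-dose SAE, followed by simple arithmetic on size.

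**Event windows, side by side**

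| Item | Start | End |
|---|---|---|
| SAE collection (Protocol 8.4.1; Table 1 footnote 14 in both documents) | Informed consent | 90 days after last dose |
| TEAE, Protocol 8.2 | After first dose of any study treatment | None stated |
| TEAE, SAP 8.3.1 | Day 1 of study treatment | On-study period, no number of days |
| TEAE, SAP 12.6.1 | After first dose | 30 days after last dose |
| SAE table, SAP 12.6.2 | None stated | None stated |

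With no limit of its own, the 12.6.2 table takes in everything collected in the active reporting period. Compared with the TEAE window in SAP 12.6.1 it adds:

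- the whole pre-dose period, which is up to 28 days of screening, or longer if consent was earlier;
- 90 − 30 = 60 days at the end, that is, SAEs on days 31 to 90 after the last dose.

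**Does another rule remove the pre-dose events?**

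1. SAP 7.4 and 12.6 use the Safety population, which is anyone given a dose of either drug. This selects patients and does not look at event dates.
2. SAP 12.0 leaves screen failures out of all tables and listings. This removes patients who were never dosed; those later dosed stay in with all their SAEs.
3. No other sentence in SAP 12.6 sets an onset rule for SAEs.

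Nothing removes them.

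**Size**

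The documents give no rate of SAEs before dosing, so the effect cannot be derived. By definition, a patient whose only SAE came before dosing is not among those with an on-treatment SAE, so the effect is additive: reported rate = on-treatment rate + p, where p is the percentage of treated patients with an SAE only before dosing. If p is assumed to be 1%, 3% or 5%, the table is 1, 3 or 5 percentage points too high.

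The effect of a single such patient depends on the column:

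- Dose level of 6 (Protocol 3.1.2 allows expansion to at least 6): 1/6 = 16.7 points.
- All of Phase 1, about 24 patients: 1/24 = 4.2 points.
- Phase 2 dose level, pooled across phases as SAP 12.6 directs. Assuming Stage 1 enrolment only and 6 Phase 1 patients at that dose: 9 + 9 + 9 + 17 + 6 = 50, and 1/50 = 2.0 points.
- A column of 100 patients (illustration): 1/100 = 1.0 point.

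**The case against.** The best reply is that the missing qualifier is shorthand. SAP 12.6.1 drops it elsewhere: it plans a breakdown of each adverse event by SOC and PT and then, as similar summaries, names TEAEs. The SAE rows of the overview sit inside a TEAE summary. Where the SAP wants events that are not treatment-emergent, as in the listing of all AEs, it says so. This reading is plausible, but the text does not establish it. Section 12.6.2 uses the qualifier for deaths and omits it for SAEs, and a programmer would have to guess. The table shells are in a separate document, and a final SAP is due before database lock; either might settle the matter, but neither is available here.

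Five other points limit the concern, and they stand:

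- Only patients with a screening SAE who were still dosed are affected. Exclusion criterion 24 and the screen-failure rule make that group small.
- An eligibility biopsy may be done before consent and serial biopsy is optional, so biopsy complications are a weak example.
- The drug-related SAE tables should be nearly untouched, because an event before any dose should not be attributed to either drug.
- Section 9 of the protocol lets the SAP modify its plans. This is an undeclared departure and is not a prohibited one.
- The SAE listing and the listing of all AEs already show individual events. They do not correct a percentage in a table.

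A reader might infer bias against the 26.1% SAE rate that the protocol quotes for the durvalumab NSCLC study. The documents do not support that: the figure comes with no stated treatment-emergent limit, and no such comparison is planned. Nor is the effect to be read on a cohort of 17. That is an efficacy sample size, and safety is tabulated by dose level.

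**Conclusion.** The point holds in a limited form. As written, SAP 12.6.2 produces an all-cause SAE table that includes screening events in patients later dosed, where Protocol 9.5.1 specifies treatment-emergent SAEs, and the table can disagree with the overview in 12.6.1.

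The direction of any error is upward. Its size is unknown: it rests on a pre-dose SAE rate that the documents do not give. It could matter at a small Phase 1 dose level and is minor once patients are pooled at the Phase 2 dose.

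It would go too far to infer that the sponsor chose to count pre-dose events as toxicity of the combination. The text shows an unstated onset rule; it does not show that intention.

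**What to change.** Replace the SAE table sentence in SAP 12.6.2 with wording such as:

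> SAEs with onset on or after the first dose of either study drug through 90 days after the last dose will be summarized by SOC and PT; SAEs with onset before the first dose will be listed separately.

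Then:

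- Apply the same start and end rule to the SAE rows of the 12.6.1 overview, so that the two tables agree.
- State that this SAE window is distinct from the 30-day TEAE window in 12.6.1. Do not label it treatment-emergent unless the two end dates are first reconciled.

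Changing SAEs to TESAEs under the SAP's 30-day definition would be the wrong repair. It would remove the pre-dose events but also drop SAEs on days 31 to 90 after the last dose, which the protocol collects and which its own treatment-emergent definition, having no end limit, would keep.

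The cost is a few sentences in the SAP and one date filter applied to two outputs. No new data are needed, and the change can go into the final SAP before database lock.
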